OC	Observed Cases
PGA	Physician's Global Assessment
PSO	Plaque Psoriasis
PT	Preferred Term
QD	Once a Day
SAE	Serious Adverse Event
SAP	Statistical Analysis Plan
SD	Standard Deviation
SOC	System Organ Class
SOP	Standard Operating Procedures
TEAE	Treatment-Emergent Adverse Event
TLF	Tables, Listings, and Figures
USPI	United States Prescribing Information
WHO	World Health Organization

CONFIDENTIAL Page 6/21

1. INTRODUCTION

This statistical analysis plan (SAP) for the final analysis is based on the most recent approved clinical study protocol (Version 1.0 dated on 01 November 2022), electronic case report form (eCRF) (Version 1.0 dated on 27 February 2023), eCRF completion guidelines (CCG, Version 1.0 dated on 01 Mar 2023), and Data Management Plan (DMP, Version 2.0 dated on 07 Mar 2023).

This SAP (Methods) documents the planned statistical analyses and data presentations for the final analysis of study DMVT-505-4002. This SAP will be finalized and approved prior to the database lock. Any deviations from this plan will be documented in the clinical study report (CSR).

2. STUDY OBJECTIVES

2.1. Primary Objective

The primary objective of the study is to evaluate the efficacy of VTAMA (tapinarof) cream, 1% in adults with plaque PSO in the head and neck region.

2.2. Secondary Objectives

The secondary objective of the study is to assess onset of effect of VTAMA (tapinarof) cream, 1% in adults with plaque PSO in the head and neck region.

2.4. Safety Objectives

The safety objective of the study is to evaluate the safety and tolerability of VTAMA (tapinarof) cream, 1% in adults with plaque PSO in the head and neck region.

[figure not shown]
CONFIDENTIAL Page 7/21

3. STUDY DESIGN

3.1. Overall Design

This is a single-group, open-label, multicenter study to evaluate the safety and efficacy of VTAMA (tapinarof) cream, 1% in the treatment of plaque PSO in the head and neck region. Participants will treat plaque PSO in the head and neck region with VTAMA (tapinarof) cream, 1% QD for 12 weeks. Efficacy of the treatment of plaque PSO in the head and neck region will be assessed with a PGA evaluation of a target lesion selected as representative of the participant's disease in the head and neck region.

Participants will be allowed to treat plaque PSO in other body areas according to instructions provided in the USPI, but no assessments of efficacy will be performed outside of the head and neck region. Safety and tolerability will be assessed by evaluation of AEs and

Study duration:

- The study duration will be up to 17 weeks.
- The treatment duration will be up to 12 weeks.
- The follow-up period will be up to 1 week.

CONFIDENTIAL Page 8/21

3.2. Study Assessments

Please refer to protocol Section 8 for descriptions of study procedures and assessments and protocol section 1.3 for timing of procedures and assessments (Schedule of Activities).

3.3. Assignment to Study Intervention

Not applicable.

3.4. Blinding

This is an open-label study.

4. SAMPLE SIZE DETERMINATION

The sample size for this study is based on clinical considerations only. No formal sample size calculation will be performed. A total of 30 participants is planned for this study which is considered adequate to evaluate the efficacy and safety for the treatment of plaque PSO in the head and neck region.

5. STATISTICAL CONSIDERATIONS

5.1. General Considerations

will perform the statistical analysis of the data. SAS version 9.4 or higher will be used to generate all statistical outputs (tables, listings, figures [TLFs], and datasets). The International Council for Harmonisation (ICH) numbering convention will be used for all TLFs. Continuous endpoints will be summarized by presenting the number of observations, means, standard deviations, medians, minimums, and maximums. The 95% confidence intervals will be reported as appropriate.

Time to event analyses will use the Kaplan-Meier product limit method (if estimable) based on observed cases.

Categorical endpoints will be summarized by presenting counts and percentages of subjects in corresponding categories. 95% confidence intervals will be reported using Clopper Pearson method as appropriate. When summarizing categorical variables, all possible categories as defined in the case report form (CRF) will be populated, even if they have zero counts. With the exception of ethnicity and race in the demographic table, percentages for missing values are omitted and do not account for the percent calculation of other categories. In certain tables (e.g., TEAEs), the total number of subjects is used as denominator. Footnotes will specify the percent basis in those cases.

will be computed and reported within EDC following the computation method outlined in protocol Section 10.6.

CONFIDENTIAL Page 9/21

Individual subject data obtained from the eCRFs and any derived data will be presented by subject in data listings.

5.2. Analysis Populations

The intent-to-treat (ITT) population will include all participants enrolled in the study.

5.3. Analysis Windowing

Study days are measured from date of first dose of study medication. Study days corresponding to measurements are calculated as:

- Assessment date date of first dose + 1 if assessment date is on or after the date of first exposure of treatment.
- Assessment date date of first dose if assessment date is before the date of first exposure of treatment.

All efficacy and safety endpoints will be analyzed according to the nominal visits (i.e. actual visit) except for assessments collected on early termination and unscheduled visits. Early termination and unscheduled visits will be re-numbered to an analysis visit based on their windowed visits defined by actual study day. If more than one visit occurs within a single visit window, then the analysis will take the one closest to the target day. If the 2 visits are equidistant from the target day, the visit with later date and time will be used.

The following analysis visit windows will apply to early termination and unscheduled visits:

Analysis Visit	Target Day	Analysis Visit Window	
Baseline (1)	1	1	
Week 1	8	Post first dose to Day 12	
Week 2	15	Day 13 – Day 22	
Week 4	29	Day 23 – Day 43	
Week 8	57	Day 44 – Day 71	
Week 12	85	Day 72 – Maximum (last day of treatment + 3 days, Day 87)	
Week 13	92	> Maximum (last day of treatment + 3 days, Day 87)	

CONFIDENTIAL Page 10/21

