6.4. Demographic and Baseline Characteristics

Demographic variables include age, sex, ethnicity, race, and Fitzpatrick skin type. Age will be reported on the CRF and will be based on age at time of signing informed consent.

Baseline characteristics (head and neck reg	gion) include	Physician Global
Assessment (PGA) for the target lesion,		

Unless otherwise noted, baseline is defined as the last non-missing value recorded before the first dose of study drug. Unscheduled visits will be used in the determination of baseline values, when applicable.

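### Does SAP 5.3 leave two possible Week 12 PGA values when an early-termination or unscheduled visit falls close to the scheduled Week 12 visit?

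*SAP*

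**What the plan says.** The primary endpoint (SAP 7.1) is the percentage of participants with a target-lesion PGA of 0 or 1 and at least a 2-grade improvement from Baseline at Week 12. SAP 5.3 decides which PGA counts as Week 12, in four steps.

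- All endpoints are "analyzed according to the nominal visits (i.e. actual visit) except for assessments collected on early termination and unscheduled visits".
- For the excepted visits: "Early termination and unscheduled visits will be re-numbered to an analysis visit based on their windowed visits defined by actual study day". The table of windows is introduced with the same scope: "The following analysis visit windows will apply to early termination and unscheduled visits".
- Where visits coincide: "If more than one visit occurs within a single visit window, then the analysis will take the one closest to the target day".
- For ties: "If the 2 visits are equidistant from the target day, the visit with later date and time will be used".

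The Week 12 target is Day 85. Its window runs from Day 72 to the later of Day 87 and three days after the last day of treatment. SAP 3.1 adds a short off-treatment phase: "The follow-up period will be up to 1 week".

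SAP 5.1 specifies Clopper-Pearson intervals, SAP 4 plans 30 participants, and SAP 5.4 rules out inferential testing.

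**The concern.** The nominal-visit sentence and the scope of the windows suggest that a scheduled Week 12 PGA is left alone. The closest-to-target sentence speaks of any visit in a window, with no limit by type.

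Take a participant whose scheduled Week 12 visit is on Day 82, when dosing stops, and who has an unscheduled or early-termination PGA on Day 86. The second PGA is re-numbered to Week 12. If the scheduled PGA stands, Day 82 is analysed. If the two compete, Day 86 is analysed, being 1 day from target instead of 3. The value used would then have been taken after dosing ended.

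At stake is the primary responder count in a small, open-label study. Two programmers could reach different counts, and the choice could be made with the scores visible.

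**Working it through.** There is no figure in the plan to reproduce, since the sample size rests on clinical considerations. The check applies the SAP 5.3 rules day by day and then sizes the effect of one changed classification.

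**Inputs.** Target Day 85; window end = max(last treatment day + 3, 87); nearest to target wins, later visit on a tie (all SAP 5.3). N = 30 (SAP 4). Assumption: the last dose is on the day of the scheduled Week 12 visit, s.

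**Later extra visit.** If scheduled and re-numbered records compete, a PGA on a later day u replaces the scheduled one when |u − 85| ≤ |s − 85| and u is inside the window.

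| Scheduled PGA (s) | Distance from 85 | Window end | Later days that replace it |
|---|---|---|---|
| Day 82 | 3 | max(85, 87) = 87 | 83 to 87 |
| Day 83 | 2 | max(86, 87) = 87 | 84 to 87 |
| Day 84 | 1 | max(87, 87) = 87 | 85, 86 |
| Day 85 | 0 | max(88, 87) = 88 | none |

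In these rows the replacing PGA is 1 to 5 days after the last dose (87 − 82 = 5 at most). For a scheduled visit after Day 85, no later PGA replaces it.

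**Earlier extra visit.** The mirror case is a scheduled visit after Day 85 with an unscheduled PGA before it. A tie now keeps the scheduled (later) record, so the earlier PGA must be strictly closer: |u − 85| < s − 85. For s = 86 that is Day 85; for s = 87, Days 84 to 86; for s = 88, Days 83 to 87. Here the replacing PGA comes before the end of treatment, so the competing reading does not always favour an off-treatment score.

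**Reading the section as a whole.** The nominal-visit sentence and the window sentence attach labels. Neither chooses between two records with the same label, so neither supplies an answer that rivals the closest-to-target rule. Taken in order (label, re-number, choose the closest, later on a tie), the section gives one Week 12 record per participant without adding anything. The alternative, scheduled record first, also gives one record but needs a precedence that the text does not state.

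**Size.** One changed classification moves the rate by 1/30 = 3.3 points. As an illustration with assumed counts: 15/30 = 50.0% (95% Clopper-Pearson 31.3 to 68.7) against 16/30 = 53.3% (34.3 to 71.7). The shift is small against an interval 68.7 − 31.3 = 37.4 points wide.

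**Conditions for any shift.** (i) The scheduled visit is off Day 85; (ii) the same participant has an extra visit in the Week 12 window; (iii) it lies close enough to Day 85 to win; (iv) a target-lesion PGA is taken at it; (v) the two PGAs differ in responder status. Visit tolerances, and whether a PGA is taken at such visits, would be in the schedule of activities, which is not shown. SAP 6.4 says "Unscheduled visits will be used in the determination of baseline values, when applicable", but that is a general baseline rule and does not establish that a PGA is taken at extra visits around Week 12.

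**The case for a change.** The strongest case for a change is that record selection for a primary endpoint should be fixed in advance, above all in an open-label study, and that one sentence before database lock would do it. The closest-to-target sentence can be narrowed in two ways: to early-termination and unscheduled visits only, or to all records labelled Week 12. The two can give different PGAs, and the SAP does not say which is meant. That much stands.

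The argument can be pushed further. With Week 12 on Day 80 and a scheduled follow-up visit on Day 87, a fully literal reading would take Day 87 (2 days from target) over Day 80 (5 days). This does not stand. A scheduled follow-up visit keeps its nominal label, and the windows apply only to early-termination and unscheduled visits, so it is never a candidate for Week 12.

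The worry about off-treatment scores carries limited weight. The window extends to at least three days after the last dose, and its Day 87 floor admits longer gaps when treatment ends early. The plan therefore accepts some post-treatment assessments as Week 12 under either convention. Scheduled-first is a reasonable preference, but nothing in the documents shows that it estimates the Week 12 response better than the pre-specified closest-to-target rule.

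**Conclusion.** No change follows. SAP 5.3 leaves a point of precedence unstated, but it does not contradict itself. Read in sequence it gives a single Week 12 value, and the other plausible convention is equally sound, so this is a detail that the analyst can settle in the programming specification.

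Each participant whose responder status depends on the choice moves the observed rate by 3.3 points with 30 evaluable. That number of participants cannot be derived and may well be zero, since several conditions must coincide in one person. No hypothesis test is planned, and no direction of bias can be shown.

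The conclusion assumes that scheduled visits keep their nominal labels, as SAP 5.3 states. The day ranges for a later extra visit also assume that dosing stops at the scheduled Week 12 visit. If dosing instead ran to Day 85 after a Day 82 visit, the window would end on Day 88 (85 + 3), and a Day 88 PGA would also replace the scheduled one on the tie rule. That adds one day to one row and does not alter the judgement.

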7.2 Participant Discontinuation/Withdrawal from the Study

- A participant may withdraw from the study at any time at the participant's own request for any reason (or without providing any reason).
- A participant may be withdrawn at any time at the discretion of the Investigator for safety or compliance reasons.
- At the time of discontinuing from the study, if possible, an early discontinuation visit should be conducted, as shown in the SoA. See SoA for data to be collected at the time of study discontinuation and follow-up and for any further evaluations that need to be completed.
- The participant will be permanently discontinued from the study product and the study at that time.
- If the participant withdraws consent for disclosure of future information, the Sponsor may retain and continue to use any data collected before such a withdrawal of consent.
- If a participant withdraws from the study, the participant may request destruction of any samples taken and not tested, and the Investigator must document this in the site study records.

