5.4. Statistical Hypotheses

Not applicable. Demographic and baseline characteristics, efficacy, safety, will be summarized descriptively. No inferential testing will be performed.

5.5. **Multiplicity Adjustment**

Not applicable

5.6. **Missing Data**

Every effort will be made to collect complete data at all visits.

All efficacy data will be summarized based on observed cases (OC).

Imputation of Missing Efficacy Data

In addition to the efficacy analysis based on OC, the primary and exploratory efficacy endpoints will also be summarized utilizing the last observation carried forward (LOCF) method to impute missing data . Baseline will not be used when applying LOCF and LOCF will be

implemented through Week 12 (i.e., Week 13 not included in LOCF). LOCF summaries will be considered supportive.

5.7. **Interim Analysis**

Not applicable

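### Could the closest-to-target visit rule in SAP 5.3 make the supportive LOCF summary carry a superseded PGA score?

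*SAP*

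**What the plan says.** SAP 5.3 opens with a general rule, "All efficacy and safety endpoints will be analyzed according to the nominal visits", and excepts assessments from ET and unscheduled visits. For those: "Early termination and unscheduled visits will be re-numbered to an analysis visit based on their windowed visits defined by actual study day". Two selection rules follow: "If more than one visit occurs within a single visit window, then the analysis will take the one closest to the target day", and "If the 2 visits are equidistant from the target day, the visit with later date and time will be used". The windows table is introduced as applying to ET and unscheduled visits.

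Under its Missing Data heading (5.6), the SAP summarises all efficacy data on observed cases, and also summarises the primary and exploratory endpoints "utilizing the last observation carried forward (LOCF) method to impute missing data". Baseline is not a source for LOCF, and carrying forward stops at Week 12. The status is stated: "LOCF summaries will be considered supportive". Text is missing straight after the words on imputing missing data, and the matching sentence in Protocol 9.3.1 is followed by redaction.

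For the secondary endpoint, SAP 5.1 says: "Time to event analyses will use the Kaplan-Meier product limit method (if estimable) based on observed cases". Protocol 7.2 asks that at withdrawal, "if possible, an early discontinuation visit should be conducted, as shown in the SoA".

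**The concern.** An ET visit will often fall in the same window as a scheduled visit already attended. If one record per window is chosen first and LOCF is run on what remains, the score taken at withdrawal can be discarded because it lies further from the target day. LOCF would then carry the older score, which is not the last observation.

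Two programmers could therefore report different LOCF responder counts from the same data. This matters somewhat because the observed-case percentage leaves missing Week 12 values out of its denominator (SAP 7.2). LOCF is the visible Week 12 responder summary that keeps early dropouts. A similar question arises for time to response: whether Kaplan-Meier uses every dated PGA or only those left after windowing.

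**Working it through.** **Inputs.** Windows and targets from SAP 5.3: Week 1, target Day 8, to Day 12; Week 2, Day 15, Days 13-22; Week 4, Day 29, Days 23-43; Week 8, Day 57, Days 44-71. Planned N = 30 (SAP 4). Clopper-Pearson intervals (SAP 5.1). The plan has no figure of its own to reproduce, as no formal sample size calculation was made and no dropout rate is given.

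**Assumptions.** Selection runs before LOCF. A scheduled visit competes with an ET visit. The scheduled visit in that window was attended. A PGA is taken at ET (the Schedule of Activities is not shown). ET days are equally likely.

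**Rule.** An ET PGA on day d, after a scheduled visit on day v in a window with target t, is dropped if |v − t| < |d − t|. On a tie the later one is kept. Example: Week 8 visit on Day 57, ET on Day 65. The distances are 0 and 8, so Day 57 is kept and carried.

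**Days on which the ET PGA is dropped**

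| Window | Visit on target | Visit 3 days early or late |
|---|---|---|
| Week 1 | Days 9-12: 4 | Day 12: 1 |
| Week 2 | Days 16-22: 7 | Days 19-22: 4 |
| Week 4 | Days 30-43: 14 | Days 33-43: 11 |
| Week 8 | Days 58-71: 14 | Days 61-71: 11 |
| Total | 39 | 27 |

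Over Days 2-71 the shares are 39/70 = 56% and 27/70 = 39%. The share depends on the denominator: 39/63 = 62% over Days 9-71, and 39/83 = 47% over Days 2-84. From Day 72 to the end of the Week 12 window, an ET PGA falls in the Week 12 window itself, so the problem is confined to earlier withdrawals.

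**Age of the carried score.** On target, the extra age sums to 10 + 28 + 105 + 105 = 248 days over 39 cases, a mean of 6.4 and a maximum of 14. With visits three days early the mean is 11.3 (maximum 17). With visits three days late it is 5.3 (maximum 11).

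**Effect on the LOCF rate.** A dropped score matters only if responder status differs between the two PGAs. Each such case moves the rate by 1/30 = 3.3 points, taking 30 in the denominator. For example, 15/30 = 50.0% (95% CI 31.3-68.7) becomes 14/30 = 46.7% (28.3-65.7).

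Expected discordant cases = dropouts before Day 72 × share dropped × discordance. With 3 dropouts and 10 to 20% discordance (both assumed):

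- low: 3 × 27/70 × 0.10 = 0.12 participants; 0.12/30 = 0.4 points
- high: 3 × 39/70 × 0.20 = 0.33 participants; 0.33/30 = 1.1 points

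Even at 50% discordance the figure is 3 × 39/70 × 0.50 = 0.84 participants, or 2.8 points. The extreme for 3 dropouts, with every score dropped and all discordant the same way, is 3/30 = 10 points. These count discordant cases. Shifts up and down can cancel, so the expected net shift is no larger.

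**The case for a change.** The strongest case for a change is that SAP 5.3 reaches every efficacy endpoint and gives ET records no exemption. Deriving analysis visits first and imputing second is a common programming order. On that reading the outcome is a defined loss of the latest score, which one added sentence would prevent. Restricting the closest-visit rule to ET and unscheduled records does not remove the problem, because a scheduled and an ET record would then share an analysis visit with no rule to choose between them.

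What stands is that the visible text does not state the order of the two steps. Several things weaken the rest:

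- The name of the method says which score is carried, and nothing visible in SAP 5.6 limits the source to window-selected records.
- Since the windows table is for ET and unscheduled visits and scheduled visits keep their nominal label, it is arguable whether the two compete at all.
- The sentence in 5.6 has a gap in the public text that may hold the rule, so silence cannot be asserted.
- The 39% and 56% are shares of calendar days, not chances of altering a result. The ET visit itself is held only where possible, and participants lost to follow-up may have none.

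The Kaplan-Meier point is of the same kind. SAP 5.1 does not spell out the input records, but time to a first response is naturally read from dated assessments. An instruction to use all post-baseline PGAs would also need an upper limit, because SAP 5.3 has a Week 13 visit after treatment ends.

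**Conclusion.** No change to the plan is needed. This is an unwritten order of operations that analysts would fill sensibly, by carrying the latest recorded post-baseline PGA up to Week 12.

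If they did not, the effect would be confined to a summary labelled supportive, in a descriptive study of 30 with no inferential testing. Under the assumptions above (three dropouts before Day 72, 10 to 20% discordance), the expected size is a third of a participant or less and about 1 point at most, with unknown direction. The 95% interval at 15/30 spans about 19 points either side. A larger shift would need several early dropouts whose status all changed the same way between two closely spaced assessments. The observed-case Week 12 result, which is the main summary of the primary endpoint, is the same whichever order is used.

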5.4. Statistical Hypotheses

Not applicable. Demographic and baseline characteristics, efficacy, safety, will be summarized descriptively. No inferential testing will be performed.

5.5. **Multiplicity Adjustment**

Not applicable

5.6. **Missing Data**

Every effort will be made to collect complete data at all visits.

All efficacy data will be summarized based on observed cases (OC).

Imputation of Missing Efficacy Data

In addition to the efficacy analysis based on OC, the primary and exploratory efficacy endpoints will also be summarized utilizing the last observation carried forward (LOCF) method to impute missing data . Baseline will not be used when applying LOCF and LOCF will be

implemented through Week 12 (i.e., Week 13 not included in LOCF). LOCF summaries will be considered supportive.

5.7. **Interim Analysis**

Not applicable

